Sample Collections	Screening/ Cycle 1 Day 1 ^a	Cycle 2 Day 1	Cycle 4 Day 1, Every 3 Cycles Thereafter, and as Clinically Indicated (\pm 7 Days) ^c	Final Visit/Time of Relapse	Comments
Mandatory Samples					
Bone Marrow Aspirate for Disease Assessment (MRD) ^b	X	X	X	X	1 – 2 mL bone marrow aspirate
Bone Marrow Aspirate for Mutational Profiling	X			X	1 – 2 mL bone marrow aspirate
Bone Marrow Aspirate for Ex Vivo sensitivity and translational research	X	X		X	3 mL bone marrow aspirate
Bone Marrow Aspirate for Bcl-2 Family Protein Analysis	X	X		X	1 mL bone marrow aspirate
Blood for Mutational Profiling	X			X	2.5 mL blood
Blood for Plasma	X	X	X ^f	X	4 ^d mL blood OR 12 ^d mL blood
Blood for Serum	X	X	X ^f	X	3.5 mL blood
Blood for Ex Vivo Sensitivity and Translational Research	X	X		X	8 mL blood
Blood for Bcl-2 Family Protein Analysis	X	X		X	2 mL blood
Pharmacogenetics	X ^e		X ^e	X	4 mL blood
Bone Marrow Core Biopsy for BCL-2 IHC	X			X	4 – 10 slides

a. Sample may be performed at Screening or Cycle 1 Day 1 prior to dosing.

Table 6. Schedule of Biomarker/Pharmacogenetic/Pharmacodynamic Sample Collection (Phase 1 and 2 {Including Cohort C}) (Continued)

- b. This sample should be taken from the first bone marrow aspirate draw.
- c. Only until 2 consecutive samples show a CR.
- d. Blood for Plasma: 4 mL blood at Screening/Cycle 1 Day 1, Cycle 2 Day 1, and Final Visit/Time of Relapse; 12 mL blood at Cycle 4 Day 1 and every 3 Cycles Thereafter.
- e. Pharmacogenetics should be collected on Cycle 1 Day 1, Cycle 4 Day 1, and Final Visit.
- f. Subjects who achieve 2 consecutive CR assessments and no longer require a bone marrow aspirate/biopsy for disease assessment, will still have plasma and serum collections at every 3 cycles thereafter.

Table 7. Schedule of Blood Collection for Venetoclax and Cytarabine Assay (Pharmacokinetic Sampling) – Phase 1 Only

Procedures	Cycle 1				Cycle 2, Cycle 4 and Every 3 Cycles Thereafter (\pm 7 Days)
	Day 1	Days 2 – 6	Day 10	Day 18	Day 1
Venetoclax		8 hours post-dose ^a	0 (pre-dose), 2, 4, 6, 8 and 24 hours post-dose	0 (pre-dose), 2, 4, 6, 8 and 24 hours post-dose	0-hour (pre-dose)
Cytarabine ^b	0 hour (pre-dose) and at 15 and 30 min and 1, 3, 6 hours following the SC dose		0 hour (pre-dose) at and 15 and 30 min and 1, 3, 6 hours following the SC dose		

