Bone marrow aspirates should be drawn into appropriately labeled tubes in conjunction with the clinical assessments. A portion of the aspirate must be processed according to the institutional standard procedures for diagnostic evaluation; however, approximately 6 to 8 mL of the bone marrow aspirate should be collected for biomarker assessments. Subjects, who achieve 2 consecutive CR assessments and no longer require a bone marrow aspirate/biopsy for disease assessment, will also not require bone marrow aspirates for biomarker collections. Detailed processing will be as outlined in the most current version of the Study M14-387 Laboratory Manual for the following:

Minimal Residual Disease Assessment

Minimal Residual Disease Assessment aspirate samples will be collected, processed and shipped to the central laboratory per the most current version of the Study M14-387 Laboratory Manual.

NOTE: This should be the first tube drawn from the bone marrow aspirate collection.

- Screening (preferred) or prior to the first dose of study drug
- Cycle 2 Day 1
- Response assessments: Cycle 4 Day 1, and every 3 cycles thereafter
- Final Visit/Time of Relapse

Mutational Profiling

Mutational Profiling will be collected at:

- Screening (preferred) or prior to the first dose of study drug
- Final Visit/Time of Relapse

Bcl-2 Family Protein Analysis

Bcl-2 Family Protein Analysis will be collected at:

- Screening (preferred) or prior to the first dose of study drug
- Cycle 2 Day 1
- Final Visit/Time of Relapse

Ex vivo sensitivity and Translational Research (e.g., BH3 profiling)

Ex vivo sensitivity and Translational research will be collected at:

- Screening (preferred) or prior to the first dose of study drug
- Cycle 2 Day 1
- Final Visit/Time of Relapse

Bone Marrow Core Biopsy for Bcl-2 IHC

A portion of the core biopsy (applicable only to counties/individual sites where this procedure is included as standard of care) must be processed for according to the institutional standard procedures for diagnostic evaluation: however, if tissue remains approximately 4 to 10 slides from the biopsy should be collected for immunohistochemistry analysis at:

- Screening (preferred) or prior to the first dose of study drug
- Final Visit/Time of Relapse

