- CRh: all of the following criteria are met: Bone marrow with $< 5\%$ blasts, peripheral neutrophils of $\geq 0.5 \times 10^3/\mu\text{L}$, and peripheral platelets $\geq 0.5 \times 10^5/\mu\text{L}$ **

* Transfusion independence is defined as the absence of any RBC or platelet transfusion during any consecutive 8 weeks during the treatment period.³⁹

** For a bone marrow sample collected before the last cycle of study treatment, the hematology lab results collected from the date of bone marrow sample collection up to Day 1 of a subsequent cycle of study treatment will be used for CRh analysis. For a bone marrow sample collected during or after the last cycle of study treatment, the hematology lab results collected within 14 days after bone marrow sample collection date will be used for CRh analysis.

Reporting of Results

All dosed subjects will be assessed for response to treatment based on the published guidelines. Assessments will be performed at Cycle 2 Day 1, Cycle 4 Day 1, and every 3 cycles thereafter for response assessment until two successive bone marrow samples document a CR. When additional bone marrow evaluations are routinely indicated for clinical management, additional collection of bone marrow aspirate and peripheral blood are strongly encouraged as these findings have the potential to define either remission status or potential progression of leukemia. NOTE: For subjects who achieve CR or CRi, MRD status may be determined.

Subjects will be assigned to one disease state for best IWG response assessment, achievement of protocol defined hematologic response, and minimal residual disease positivity at the time of the best response.

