8.1.3 Efficacy Summaries

Efficacy will include analyses of ORR as defined by CR + CRi + PR, CR rate, CRi rate, CRh rate, CR + CRi rate, CR + CRh rate, DOR, EFS, OS, the exploratory analysis of the proportion of for all subjects who achieve MRD negativity, the proportion of subjects who are transfusion independent post baseline, and the proportion of subjects who undergo subsequent stem cell transplant. Transfusion support needs will be recorded to define ongoing transfusion dependence.

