8.1.3.1.5 MRD Negativity Rate

The proportion of subjects who reach MRD negativity in this exploratory measurement and the duration of this status will be summarized.

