8.1.12 Exploratory Analysis of MRD Data

The MRD data is collected at baseline, the end of Cycle 1, and every 3 cycles thereafter when bone marrow is collected in Study M14-358 and Study M14-387. The MRD data collected after the first dose of study drug to the last dose of study drug + 7 days, disease progression, clinical progression, the start of new post-treatment therapy, death, or cutoff date, whichever occurs earlier, will be included in the post-baseline MRD analyses.

The MRD analyses include MRD records meeting the following criteria:

1. CD45 value \geq 100,000 and MRD value $<$ 0.1%; or
2. MRD value \geq 0.1%.

Zero is imputed if MRD value is 'less than LLoQ.' Missing MRD is assigned if MRD value is 'too few CD45+ cell.'

The best post-baseline MRD (the lowest) value will be defined as the smallest MRD collected after the first dose of study drug to the last dose of study drug + 7 days, disease progression, clinical progression, the start of new post-treatment therapy, death, or cutoff date, whichever occurs earlier. The median and range will be presented for subjects who

achieved CR, CR + CRh or CR + CRi. The best MRD value will also be categorized to three groups $< 0.1\%$, $\geq 0.1\%$, and Unknown/Missing MRD value. The summary of the best MRD value will be performed among subjects who achieved CR, CR + CRh, or CR + CRi.

OS will also be summarized by the best MRD value ($< 0.1\%$, $\geq 0.1\%$, Unknown/Missing if any) for subjects achieved CR + CRh or CR + CRi. Median survival time with the corresponding 95% CI will be provided from Kaplan-Meier estimation.

OS will also be summarized by the best MRD value ($< 1\%$, $\geq 1\%$, Unknown/Missing if any) for subjects achieved CR + CRh or CR + CRi. Median survival time with the corresponding 95% CI will be provided from Kaplan-Meier estimation.

Duration of CR + CRh will also be summarized by the best MRD value ($< 0.1\%$, $\geq 0.1\%$, Unknown/Missing if any) for subjects achieved CR + CRh. Median duration of CR + CRh with the corresponding 95% CI will be provided from Kaplan-Meier estimation.

Duration of CR + CRi will also be summarized by the best MRD value ($< 0.1\%$, $\geq 0.1\%$, Unknown/Missing if any) for subjects achieved CR + CRi. Median duration of CR + CRi with the corresponding 95% CI will be provided from Kaplan-Meier estimation.

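### Three sections define MRD status differently, and the SAP splits OS and response duration by the lowest on-treatment MRD value with no landmark, which favours the < 0.1% group

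*SAP*

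**What the plan says.** SAP 8.1.12 sets the classifier: "The best post-baseline MRD (the lowest) value will be defined as the smallest MRD collected after the first dose of study drug". The window ends at the first of last dose + 7 days, disease or clinical progression, new post-treatment therapy, death or cutoff ("whichever occurs earlier, will be included in the post-baseline MRD analyses"). A result below 0.1% counts only with a CD45 value of at least 100,000, while every result of 0.1% or more is kept. Samples with too few cells are set to missing.

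The value is summarised for CR, CR + CRh and CR + CRi. OS is split by it at 0.1% and again at 1%, and the durations of CR + CRh and CR + CRi at 0.1%. No landmark is stated. OS runs from first dose (SAP 8.1.7).

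The protocol speaks to MRD status in two ways. Section 5.3.3, on reporting of results, assigns each subject "minimal residual disease positivity at the time of the best response". Section 8.1.3 lists the proportion of subjects "who achieve MRD negativity", and 8.1.3.1.5 says: "The proportion of subjects who reach MRD negativity in this exploratory measurement and the duration of this status will be summarized". Neither of the last two fixes a time point.

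On sampling, protocol 5.3.1.5 schedules post-baseline MRD aspirates at Cycle 2 Day 1 and then "Response assessments: Cycle 4 Day 1, and every 3 cycles thereafter", plus the final visit or relapse. Table 6, footnote c, limits the series from Cycle 4 Day 1 on: "Only until 2 consecutive samples show a CR". Section 5.3.1.5 repeats the stop: "Subjects, who achieve 2 consecutive CR assessments and no longer require a bone marrow aspirate/biopsy for disease assessment, will also not require" marrow aspirates for biomarkers. CRi and CRh are not named as triggers.

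**The concern.** A lowest-value rule does not tie MRD status to the marrow that documents the response. A subject who reads < 0.1% at Cycle 2 Day 1 and 0.5% at the marrow documenting CR at Cycle 7 Day 1 would be reported as a CR with MRD < 0.1%. Under protocol 5.3.3 the same subject is positive.

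A minimum also depends on how many samples feed it, and here that number depends on time on treatment and on type of response. When OS and response duration are then split by the minimum, a subject who stays alive, progression-free and on treatment may have more chances to enter the favourable group. Part of any apparent advantage for MRD < 0.1% would come from the way the groups are formed.

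**Working it through.** The documents state no MRD rate, target or power, so there is no planned figure to reproduce.

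**1. The definitions side by side.**

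| Source | Sample that sets the status | Population |
|---|---|---|
| Protocol 5.3.3 | the one at best response | each subject |
| Protocol 8.1.3, 8.1.3.1.5 | none fixed; fits ever negative; duration also wanted | all subjects |
| SAP 8.1.12 | lowest in the on-treatment window; no duration of negativity | responders |

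The protocol does not agree with itself, and the SAP matches neither version in full.

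**2. Direction.** If the marrow at best response has an evaluable MRD result and lies inside the SAP window, its value is one of those over which the minimum is taken. So the minimum is no higher than that value. In these subjects the share below 0.1% under the SAP rule cannot be smaller than under protocol 5.3.3.

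**3. Number of scheduled samples.** Visits are Day 1 of Cycles 2, 4, 7, 10 and 13. Sampling stops at the second consecutive CR; the table assumes that a CR, once seen, is confirmed at the next marrow.

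| Last marrow visit reached | CR first at C2 | at C4 | at C7 | at C10 | CRi/CRh, no CR |
|---|---|---|---|---|---|
| C4D1 | 2 | 2 | – | – | 2 |
| C7D1 | 2 | 3 | 3 | – | 3 |
| C10D1 | 2 | 3 | 4 | 4 | 4 |
| C13D1 | 2 | 3 | 4 | 5 | 5 |

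Against the earliest CRs the CRi/CRh excess is 2 − 2 = 0 through C4D1, then 3 − 2 = 1, 4 − 2 = 2 and 5 − 2 = 3 at C7, C10 and C13. Standard-of-care marrows (protocol 5.3.1.1) and a final-visit sample inside the window would add to these counts.

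**4. Possible size.** Let p be the chance that one sample reads < 0.1%, and k the number of samples. If samples are independent, P(at least one < 0.1%) = 1 − (1 − p)^k. At p = 0.20 this is 1 − 0.8² = 36.0% for k = 2 and 1 − 0.8⁵ = 67.2% for k = 5. For correlated samples I used a one-factor normal model with latent correlation ρ: the average over a standard normal Z of 1 − (1 − q)^k, where q = Φ[(Φ⁻¹(p) − √ρ·Z)/√(1 − ρ)]. Both p and ρ are assumptions. Cells show k = 2 versus k = 5.

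| p (rate with one sample) | ρ = 0 | ρ = 0.8 | ρ = 0.9 |
|---|---|---|---|
| 10% | 19.0% vs 41.0% | 14.4% vs 21.0% | 13.1% vs 17.4% |
| 20% | 36.0% vs 67.2% | 27.1% vs 36.6% | 25.0% vs 31.3% |
| 30% | 51.0% vs 83.2% | 38.9% vs 49.8% | 36.2% vs 43.6% |
| 40% | 64.0% vs 92.2% | 49.9% vs 61.1% | 46.9% vs 54.7% |

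At p = 20% the gap between 2 and 5 samples is 31.2 points if independent, 9.5 at ρ = 0.8 and 6.3 at ρ = 0.9.

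**5. The outcome splits.** OS is counted from first dose, but group membership is settled only when the last MRD sample in the window is read. A subject first reading < 0.1% at C7D1 has to be alive and free of progression until then, and that time is credited to the < 0.1% group. Response duration has the same fault whenever the lowest sample comes after the response date. The two-CR stop limits the effect in early CRs but does not remove it: a CR at C2 must still be on treatment at C4D1 to give a second scheduled sample.

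**The case against.** A reader might infer that the SAP overrides a settled protocol definition, inflates every MRD rate, and biases the comparison against CR. The documents do not support that.

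- Protocol 8.1.3 and 8.1.3.1.5 are the statistical sections on MRD, and their wording fits an ever-negative reading. The lowest value is inflated only relative to 5.3.3.
- The minimum is not unlimited in time. The window closes at progression, new therapy, death, cutoff or last dose + 7 days, and the CD45 rule discards < 0.1% readings based on too few cells.
- CRi and CRh subjects do not in general have more chances. There is no scheduled excess through C4D1 and little or none against late CRs, and a CRi or CRh subject who stops early has fewer samples. Two versus five is the extreme pairing.
- The summary groups are nested. There is no CRi-only or CRh-only row, and the outcome splits use the combined sets, so unequal sampling shows only indirectly.
- Serial marrows from one subject are unlikely to be independent, so the larger gaps in the table are upper illustrations.
- The analysis is labelled exploratory, and SAP 9.0 plans no formal testing.

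All of this stands and lowers the priority. It does not reconcile the sections, and neither the window nor the CD45 rule deals with the missing landmark.

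**Conclusion.** The concern holds in a limited form. Protocol 5.3.3, protocol 8.1.3/8.1.3.1.5 and SAP 8.1.12 do not give one MRD status. The direction of the difference is certain in subjects evaluable at best response: the SAP rule gives a < 0.1% rate at least as high as the 5.3.3 status. The sample count depends on time on treatment and, from C7D1, on response type, so the unlandmarked OS and duration splits favour the < 0.1% group through immortal time.

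The size cannot be derived from the documents. At an assumed 20% per sample, moving from 2 to 5 samples raises the rate by about 31 points if samples are independent and by about 6 to 10 points at correlations of 0.8 to 0.9. Priority is low to moderate because the analysis is exploratory and descriptive.

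**What to change.** - Reconcile protocol 5.3.3, protocol 8.1.3.1.5 and SAP 8.1.12, and say which status each table uses.
- In SAP 8.1.12, add MRD status from the marrow that documents the subject's best response, under the existing CD45 and 0.1% rules. CRh is derived and is not an IWG category, so name its marrow explicitly: the one used in the CRh derivation.
- Use that status for the OS and duration splits, counting time from that marrow date or from another stated landmark. Changing the MRD definition alone would not be enough, because status at best response is also fixed after first dose.
- Keep the lowest value as a row labelled as ever reached, with the number of evaluable MRD samples per subject shown by best response.

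The cost is SAP wording and re-derivation from samples already assayed. The price is a < 0.1% rate that may be lower, a few more missing values where the response marrow has no evaluable MRD, and the loss of subjects with events before the landmark.

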8.1.13 Subgroup Assessment of Efficacy Variables

The subgroup analyses will be performed for Studies M14-358 and M14-387 including the following treatment groups.

Study M14-358:

1. overall of venetoclax + azacitidine (N = 127)
2. venetoclax 400 mg + azacitidine (N = 84)
3. overall of venetoclax + decitabine (N = 73)

Study M14-387:

1. venetoclax 600 mg QD + LDAC or venetoclax 800 mg QD + LDAC (N = 92)
2. venetoclax 600 mg QD + LDAC (N = 82)
3. venetoclax 600 mg QD + LDAC and without MPN (N = 78).

No subgroup analyses will be performed for Study M14-212 due to relative small number of patients in this study.

CR rate, CR + CRh rate, post-baseline transfusion independence rate, duration of CR, duration of CR + CRh, and OS will be assessed for the subgroups within each treatment group as defined below.

- Gender (Male, Female)
- Age (< 75 years, ≥ 75 years)
- By modified Ferrara Criteria (Y, N)
- By Cytogenetics (Intermediate risk, poor risk)
- Type of AML (primary, secondary)
- AML MDS related changes (Yes, No)
- Prior HMA use (Yes, No) (only for Study M14-387)
- Biomarker mutation (TP53, FLT3, IDR1/2, NPM1)
- Moderate/Strong CYP3A inhibitors (Y, N)

In addition, number of percentage of CR/CRh subjects went on post-treatment therapy will be summarized.

9.0 Sample Size

For the non-randomized Phase 1/2 Studies M14-358 and M14-387, there is no formal statistical testing and study-wise sample size justification planned. Sample size justification for the Expansion 1 and Expansion 2 cohorts of Study M14-358 based on

CR + CRi rate and the Phase 2 portion of Study M14-387 based on ORR rate can be found in each study protocol. The full analysis set of Study M14-358 and Study M14-387 includes both dose escalation and dose expansion. The sample size justification using CR rates at the recommended Phase 2 venetoclax dose level for Study M14-358 and Study M14-387 and historical CR rates are summarized in [Table 7](#).

Table 7. Sample Size Justification

	N	Targeted CR Rate (95% CI)	Historical CR Rate of LDAC Alone (%) ¹	Historical CR Rate of AZA Alone (%) ¹	Historical CR Rate of DEC Alone (%) ²
Study M14-387 venetoclax 600 mg QD + LDAC	82	21% (13%, 31%)	7.9%	NA	NA
Study M14-358 venetoclax 400 mg QD + AZA	84	36% (27%, 48%)	NA	19.5%	NA
Study M14-358 venetoclax 400 mg QD + DEC	31	39% (22%, 58%)	NA	NA	15.7%

Based on the enrolled sample sizes in Studies M14-358 and M14-387, the lower limit of the 95% confidence intervals for the target CR rates are higher than the historical CR rates from previously conducted clinical trials of azacitidine, decitabine and LDAC, and represent a clinically meaningful improvement for subjects.

2.1 Summary of Versions

Version	Date of Completion	Summary
1.0	13 Dec 2017	First version (Appendix of Briefing Book of FDA Type C Meeting)
2.0	04 May 2018	Final version for Interim 1 CSR
3.0	27 Nov 2018	Update MEDDRA version for Interim 2 CSR

2.2 List of Abbreviations and Definitions of Terms

AE	Adverse event
AESI	Adverse Event of Special Interest
ALC	Absolute lymphocyte count
ALT	Alanine aminotransferase
AML	Acute Myeloid leukemia
AST	Aspartate aminotransferase
HMA	Azacitidine or Decitabine
ISS	Integrated summary of safety
LDAC	Low dose cytarabine
MedDRA	Medical dictionary for regulatory activities
MPN	Myeloproliferative neoplasm
NCI	National Cancer Institute
NCI CTC	National Cancer Institute Common Terminology Criteria
PT	Preferred term
RBC	Red blood cells
SAE	Serious adverse event
SAP	Statistical analysis plan
SMQ	Standardized MedDRA query
SOC	System organ class
TEAE	Treatment-emergent adverse event
ULN	Upper limit of normal
WBC	White blood cells
WHO	World Health Organization

3.0 Introduction

This safety statistical analysis plan (SAP) covers analyses of safety data from Studies M14-358 (R&D/17/1341), M14-387 (R&D/17/1340), and M14-212 (R&D/15/0200). These analyses will support the safety assessment of venetoclax for AML. Analyses will be performed by personnel from Data and Statistical Sciences at AbbVie or their designees using SAS Version 9.3 or later (SAS Institute Inc., Cary, NC 27513) under the UNIX operating system.

4.0 Study Background

This SAP provides details of statistical analyses that are to be performed for the safety assessment of venetoclax treatment for AML. Safety analyses will be performed to assess the potential effect of venetoclax monotherapy or in combination with hypomethylating agents (HMA) or low dose cytarabine (LDAC) on adverse events (AEs), as well as clinical laboratory measurements and vital signs.

5.0 Studies Included

All AbbVie sponsored venetoclax AML studies to be included are described below in [Table 1](#). All studies' results will be presented separately. Data will not be pooled across studies.

Table 1. List of Venetoclax Studies to be Included in the Safety Summary

Study ID Phase (Status)	Number of Enrolled Subjects (Actual/Planned)	Location	Study Design	Primary Objective
M14-212 Phase 2 (completed)	32/54	US	Open-label study of venetoclax in adults with relapsed or refractory AML, or untreated AML unfit for intensive therapy	Evaluate the preliminary efficacy of single agent venetoclax.
M14-358 Phase 1b (Enrollment complete and follow-up is ongoing)	212/260	Australia, Germany, France, and US	Open-label study of venetoclax + azacitidine or decitabine in treatment naïve elderly (≥ 60 years) subjects with AML who are not eligible for standard induction therapy; 2 stages: dose escalation and dose expansion	Evaluate the safety, PK, and efficacy of venetoclax + decitabine or azacitidine in the target population. The objective of the safety expansion is to confirm efficacy and safety of the intended dose for Phase 3 study.
M14-387 Phase 1/2 (Enrollment complete and follow-up is ongoing)	92/94	Australia, Germany, Italy, US	Open-label study of venetoclax + LDAC in treatment naïve subjects with AML who are ≥ 60 years of age and who are not eligible for standard anthracycline-based induction therapy; 2 stages: dose escalation and safety expansion	Phase 1: Evaluate the safety, PK and determine the MTD and RPTD of venetoclax + LDAC. Phase 2: Estimate efficacy, including ORR, and characterize the toxicity of the combination at the RPTD. Cohort C: Evaluate the ORR for subjects allowed additional supportive medications (strong CYP3A inhibitors) if medically indicated.

The venetoclax doses and regimens in the studies listed in [Table 1](#) are described in [Table 2](#) below.

Table 2. Regimens Investigated in Venetoclax AML Studies

Study ID	Venetoclax Dose and Frequency	Treatment Regimen
M14-212	Venetoclax 400 mg QD, 800 mg QD, 1200 mg QD	Venetoclax monotherapy
M14-358	Venetoclax 400 mg QD, 800 mg QD, 1200 mg QD	Venetoclax in combination with HMA (Azacitidine or Decitabine)
M14-387	Venetoclax 600 mg QD, 800 mg QD	Venetoclax in combination LDAC (Low dose cytarabine)

